- 8.7.b.1.** If there will be repeated interactions with the impaired subjects over a time period when cognitive capacity could increase or diminish, also describe how (if at all) decision-making capacity will be re-assessed and (if appropriate) consent obtained during that time.

The intervention of this study occurs in the initial insulin dosing on hospital admission. The rest of patient care will be no different from standard of care. After hospital discharge, there is no ongoing interaction with subjects.

- 8.7.c. Permission (surrogate consent).** If the research will include adults who cannot consent for themselves, describe the process for obtaining permission ("surrogate-consent") from a legally authorized representative (LAR).

For research conducted in Washington State, review the guidance on [Diminished and Fluctuating Consent Capacity and Use of a Legally Authorized Representative \(LAR\)](#) to learn which individuals meet the state definition of "legally authorized representative".

If subjects are not able to consent for themselves, the hospitalists or PI will ask patient's legally authorized representative (LAR) to if he/she is willing to consent for the patient.

- 8.7.d. Assent.** Describe whether assent will be required of all, some, or none of the subjects. If some, indicate which subjects will be required to assent and which will not (and why not). Describe any process that will be used to obtain and document assent from the subjects.

We will not obtain assent for the study procedure from subjects if they do not have the decision capacity to provide consent themselves.

- 8.7.e. Dissent or resistance.** Describe how a subject's objection or resistance to participation (including non-verbal) during the research will be identified, and what will occur in response.

Being in the study is voluntary. If potential subjects tell the hospitalists or PI that they do not want to participate, we will not include them in the study.

- 8.8. Research use of human fetal tissue obtained from elective abortion.** Federal and UW Policy specify some requirements for the consent process. If you are conducting this type of research, check the boxes to confirm these requirements will be followed.

- ☐ Informed consent for the donation of fetal tissue for research use will be obtained by someone other than the person who obtained the informed consent for abortion.
- ☐ Informed consent for the donation of fetal tissue for research use will be obtained after the informed consent for abortion.
- ☐ Participation in the research will not affect the method of abortion.
- ☐ No enticements, benefits or financial incentives will be used at any level of the process to incentivize abortion or the donation of human fetal tissue.
- ☐ The informed consent form for the donation of fetal tissue for use in research will be signed by both the woman and the person who obtains the informed consent.

8.9. Consent-related materials. Upload to **Zipline** all consent scripts/talking points, consent forms, debriefing statements, Information Statements, Short Form consent forms, parental permission forms, and any other consent related materials that will be used. Materials that will be used by a specific site should be uploaded to that site's Local Site Documents page.

- *Translations must be submitted and approved before they can be used. However, we strongly encourage you to wait to provide them until the IRB has approved the English versions.*
- *Combination forms: it may be appropriate to combine parental permission with consent if parents are subjects as well as providing permission for the participation of their children. Similarly, a consent form may be appropriately considered an assent form for older children.*
- *For materials that cannot be uploaded: upload screenshots or written descriptions that are sufficient to enable the IRB to understand the types of data that will be collected and the nature of the experience for the participants. URLs (website addresses) may also be provided, or written descriptions of websites. Examples of materials that usually cannot be uploaded: mobile apps; computer-administered text; licensed and restricted standardized tests.*

9. PRIVACY AND CONFIDENTIALITY

9.1. [DETERMINATION] Privacy protections. Describe the steps that will be taken, if any, to address possible privacy concerns of subjects and potential subjects.

Privacy refers to the sense of being in control of access that others have to ourselves. This can be an issue with respect to recruiting, consenting, sensitivity of the data being collected, and the method of data collection.

Examples:

- *Many subjects will feel a violation of privacy if they receive a letter asking them to participate in a study because they have ____ medical condition, when their name, contact information, and medical condition were drawn from medical records without their consent. Example: the IRB expects that ["cold contact" recruitment letters](#) will inform the subject about how their information was obtained.*
- *Recruiting subjects immediately prior to a sensitive or invasive procedure (e.g., in an outpatient surgery waiting room) will feel like an invasion of privacy to some individuals.*
- *Asking subjects about sensitive topics (e.g., details about sexual behavior) may feel like an invasion of privacy to some individuals.*

To protect privacy, identifiers and study data will be stored separately but a link will be maintained between the identifiers and the study data.

The consent interview may happen in the emergency or hospital room. At the emergency room at Montlake and Northwest hospitals, each patient has their own room, so the consent interview will be conducted in a private room. At the emergency room at Harborview hospital, patients may be only separated by curtains. The hospitalists or PI will ask if they prefer to do the consent interview in a private room.

9.2. **[DETERMINATION]** Identification of individuals in publications and presentations. Will potentially identifiable information about subjects be used in publications and presentations, or is it possible that individual identities could be inferred from what is planned to be published or presented?

☒ No

☐ Yes → Will subject consent be obtained for this use?

☐ Yes

☐ No → Describe the steps that will be taken to protect subjects (or small groups of subjects) from being identifiable.

Click or tap here to enter text.

9.3. **[DETERMINATION]** State mandatory reporting. Each state has reporting laws that require some types of individuals to report some kinds of abuse, and medical conditions that are under public health surveillance. These include:

- Child abuse
- Abuse, abandonment, neglect, or financial exploitation of a vulnerable adult
- Sexual assault
- Serious physical assault
- Medical conditions subject to mandatory reporting (notification) for public health surveillance

Are you or a member of the research team likely to learn of any of the above events or circumstances while conducting the research **AND** feel obligated to report it to state authorities?

☒ No

☐ Yes → The UW IRB expects subjects to be informed of this possibility in the consent form or during the consent process, unless you provide a rationale for not doing so:

Click or tap here to enter text.

9.4. **[DETERMINATION]** Records retention requirements. Check the box below to indicate assurance that any identifiers (or links between identifiers and data/specimens) and data that are part of the research records will not be destroyed until after the end of the applicable records retention requirements (e.g., Washington State; funding agency or sponsor; Food and Drug Administration). If it is important to say something about destruction of identifiers (or links to identifiers) in the consent form, state that identifying information will be destroyed at the end of the study or after the records retention period required by state and/or federal law.

Review the "Research Data" and "Personal Identifiers" sections of the following website for UW Records management for the Washington State research records retention schedules that apply in general to the UW (not involving UW Medicine data):

<http://f2.washington.edu/fm/recmgt/gs/research?title=R>; <https://finance.uw.edu/recmgt/gs/research?title=P>.

Review the "Research Records and Data" information in Section 8 of this document for the retention schedules for UW Medicine Records: <https://www.uwmedicine.org/recordsmanagementuwm-records-retention-schedule.pdf>

☒ Confirm

9.5. **[DETERMINATION]** Certificates of Confidentiality. Will a federal Certificate of Confidentiality be obtained for the research data? *NOTE: Answer "No" if the study is funded by NIH or the CDC, because most NIH-funded and CDC-funded studies automatically have a Certificate.*

☒ No

☐ Yes

9.6. **[DETERMINATION] Data and specimen security protections.** Identify the data classifications and the security protections that will be provided for all sites where data will be collected, transmitted, or stored, referring to the guidance on [Data and Security Protections](#) for the minimum requirements for each data classification level. ***It is not possible to answer this question without reading this document. Data security protections should not conflict with records retention requirements.***

9.6.a. Choose the level(s) of protections that will be applied to the data and specimens. If more than one level will be used, use the text box to describe which level will apply to which data and which specimens and at which sites.

- ☐ **Level 1:** Very low risk of harm if disclosed
- ☐ **Level 2:** Some risk of minor harm if disclosed
- ☒ **Level 3:** Could cause risk of material harm if disclosed
- ☐ **Level 4:** Would likely cause serious harm to individuals if disclosed
- ☐ **Level 5:** Extremely sensitive; could cause severe harm to individuals if disclosed

We believe the study data are level 3: non-sensitive personal health information. But we plan to store the study data separately from the identifier, which can make the data de-identified (level 1: very low risk of harm if disclosed).

We plan to store study data and the link (between direct and indirect identifier) separately in REDcap. Only the study members (PI [name] [name] and supervising faculty [name]) have access to the database.

9.6.b. Use this space to provide additional information, details, or to describe protections that do not fit into one of the levels. **HSD allows researchers to request exceptions to data security requirements, if the exception is necessary and does not significantly increase risk to participants.** If there are any protections within the level listed in 9.6.a which will not be followed, list those here, including identifying the sites where this exception will apply. For example, if you intend to store subject identifiers with study data (not permitted under requirement U9 for Risk Levels 3-5), then indicate this in the box below (e.g., “We will not adhere to requirement U9 for screening data”).

Click or tap here to enter text.

10. RISK / BENEFIT ASSESSMENT

10.1. **[DETERMINATION] Anticipated risks.** Describe the anticipated risks of harm, discomforts, and hazards to the subjects and others of the research procedures.

For each harm, discomfort, or hazard:

- Describe the magnitude, probability, duration, and/or reversibility of the harm, discomfort, or hazard, AND
- Describe how the risks will be reduced or managed. Do not describe data security protections here, these are already described in [question 9.6.](#)
- Consider possible physical, psychological, social, legal, and economic harms, including possible negative effects on financial standing, employability, insurability, educational advancement, or reputation. For example, a breach of confidentiality might have these effects.
- Examples of “others”: embryo, fetus, or nursing child; family members; a specific group.

- Ensure applicable risk information from any Investigator Brochures, Drug Package Inserts, and/or Device Manuals is included in your description.
- Do not include the risks of non-research procedures that are already being performed.
- If the study design specifies that subjects will be assigned to a specific condition or intervention, then the condition or intervention is a research procedure - even if it is a standard of care.
- Examples of mitigation strategies: inclusion/exclusion criteria; taking blood samples to monitor something that indicates drug toxicity.
- Review the guidance on [Identifying and Describing Reasonably Foreseeable Risks in Research](#) for information about which risks should be described in the consent process/form.
- As with all questions on this application, you may refer to uploaded documents.

There is theoretical risk of hypoglycemia when using our initial insulin dosing calculator. But the same risk exists in the standard of care as well.

Our UW observational cohort (STUDY00015475) has 1/140 patients (0.7%) who had hypoglycemia < 54 mg/dL during the first 24 hours of hospitalization. We think 3% increase (which means 3.7%) is considered clinically significant increase, so among these 85 subjects there cannot be more than $85 \times 3.7\% = 3.15$ subjects that develop hypoglycemia < 54 mg/dL. So, if we find more than 3.15 patients (round to 4) who develop BG < 54 during the recruitment, that is more than 3% increase. Because this is the first feasibility trial to apply the calculator on patients, we plan to enroll 10 subjects first, to demonstrate the calculator dose does not cause hypoglycemia (≤ 54 mg/dL). After these 10 participants are recruited, we will review and analyze these data. Then we will apply for a modification to increase the sample size.

UW inpatient insulin order set comes with hypoglycemia protocols which will be used to manage hypoglycemia if it occurs.

If hospitalists do not feel comfortable with the calculator doses when they enroll subjects, they will contact PI: [name] in real time, and we will double-check the calculator doses. If these subjects are admitted after midnight and PI: [name] is unavailable for discussion, hospitalists will not enroll the subject. Hospitalists and PI: [name] will then discuss this scenario (subject not enrolled) to understand the reasons hospitalists did not feel comfortable with the calculator dose.

10.2. [DETERMINATION] Reproductive risks. Are there any risks of the study procedures to subjects or partner of subjects related to pregnancy, fertility, lactation or effects on a fetus or neonate?

Examples: direct teratogenic effects; possible germline effects; effects on fertility; effects on a woman's ability to continue a pregnancy; effects on future pregnancies.

☒ **No** → Go to [question 10.3.](#)

☐ **Yes** → Answer the following questions:

10.2.a. Risks. Describe the magnitude, probability, duration and/or reversibility of the risks.

Click or tap here to enter text.

10.2.b. Steps to minimize risk. Describe the specific steps that will be taken to minimize the magnitude, probability or duration of these risks.

Examples: inform the subjects about the risks and how to minimize them; require a pregnancy test before and during the study; require subjects to use contraception; advise subjects about banking of sperm and ova.

If the use of contraception will be required, describe the allowable methods and the time period when contraception must be used.

Click or tap here to enter text.

10.2.c. Pregnancy. Describe what will be done if a subject (or a subject's partner) becomes pregnant.

For example; will subjects be required to immediately notify study staff, so that the study procedures can be discontinued or modified, or for a discussion of risks, and/or referrals or counseling?

Click or tap here to enter text.

10.3. [DETERMINATION] MRI risk management. A rare but serious adverse reaction called nephrogenic systemic fibrosis (NSF) has been observed in individuals with kidney disease who received gadolinium-based contrast agents (GBCAs) for the scans. Also, a few healthy individuals have a severe allergic reaction to GBCAs.

10.3.a. Use of gadolinium. Will any of the MRI scans involve the use of a gadolinium-based contrast agent (GBCA)?

☒ **No**

☐ **Yes** → Which agents will be used? *Check all that apply.*

Check all that apply	Brand Name	Generic Name	Chemical Structure
	Dotarem	Gadoterate meglumine	Macrocylic
	Eovist / Primovist	Gadoxetate disodium	Linear
	Gadavist	Gadobutro	Macrocylic
	Magnevist	Gadpentetate dimeglumine	Linear
	MultiHance	Gadobenate dimeglumine	Linear
	Omniscan	Gadodiamide	Linear
	OptiMARK	Gadoversetamide	Linear
	ProHance	Gadoteridol	Macrocylic
	Other, provide name:		

Click or tap here to enter text.

10.3.a.1. The FDA has concluded that gadolinium is retained in the body and brain for a significantly longer time than previously recognized, especially for linear GBCAs. The health-related risks of this longer retention are not yet clearly established. However, the UW IRB expects researchers to provide a compelling justification for using a linear GBCA instead of a macrocylic GBCA, to manage the risks associated with GBCAs.

Describe why it is important to use a GBCA with the MRI scan(s). Describe the dose that will be used and (if it is more than the standard clinical dose recommended by the manufacturer) why it is necessary to use a higher dose. If a linear GBCA will be used, explain why a macrocylic GBCA cannot be used.

Click or tap here to enter text.

10.3.a.2. Information for subjects. Confirm by checking this box that subjects will be provided with the FDA-approved Patient Medication Guide for the GBCA being used in the research or that the same information will be inserted into the consent form.

☐ **Confirmed**

10.3.b. Who will (1) calculate the dose of GBCA; (2) prepare it for injection; (3) insert and remove the IV catheter; (4) administer the GBCA; and (5) monitor for any adverse effects of the GBCA? Also, what are the qualifications and training of these individual(s)?

Click or tap here to enter text.

10.3.c. Describe how the renal function of subjects will be assessed prior to MRI scans and how that information will be used to exclude subjects at risk for NSF.

Click or tap here to enter text.

10.3.d. Describe the protocol for handling a severe allergic reaction to the GBCA or any other medical event/emergency during the MRI scan, including who will be responsible for which actions.

Click or tap here to enter text.

10.4. [DETERMINATION] Unforeseeable risks. Are there any research procedures that may have risks that are currently unforeseeable?

Example: using a drug that hasn't been used before in this subject population.

☒ **No**

☐ **Yes** → Identify the procedures.

Click or tap here to enter text.

10.5. Subjects who will be under regional or general anesthesia. Will any research procedures occur while patients are under general or regional anesthesia, or during the 3 hours preceding general or regional anesthesia (supplied for non-research reasons)?

☒ **No**

☐ **Yes** → Check all the boxes that apply.

- ☐ Administration of any drug for research purposes
- ☐ Inserting an intra-venous (central or peripheral) or intra-arterial line for research purposes
- ☐ Obtaining samples of blood, urine, bone marrow or cerebrospinal fluid for research purposes
- ☐ Obtaining a research sample from tissue or organs that would not otherwise be removed during surgery.
- ☐ Administration of a radio-isotope for research purposes**
- ☐ Implantation of an experimental device
- ☐ Other manipulations or procedures performed solely for research purposes (e.g., experimental liver dialysis, experimental brain stimulation)

If any of the boxes are checked:

Provide the name and institutional affiliation of a physician anesthesiologist who is a member of the research team or who will serve as a safety consultant about the interactions between the research procedures and the general or regional anesthesia of the subject-patients. If the procedures will be performed at a UW Medicine facility or affiliate, the anesthesiologist must be a UW faculty member, and

the Vice Chair of Clinical Research in the UW Department of Anesthesiology and Pain Medicine must be consulted in advance for feasibility, safety and billing.

Click or tap here to enter text.

*** If the box about radio-isotopes is checked, the study team is responsible for informing in advance all appropriate clinical personnel (e.g., nurses, technicians, anesthesiologists, surgeons) about the administration and use of the radio-isotope, to ensure that any personal safety issues (e.g., pregnancy) can be appropriately addressed. This is a condition of IRB approval.*

10.6. Data and Safety Monitoring. A Data and Safety Monitoring Plan (DSMP) is required for clinical trials (as defined by NIH). If required for this research, or if there is a DSMP for the research regardless of whether it is required, upload the DSMP to **Zipline**. If it is embedded in another document being uploading (for example, a Study Protocol) use the text box below to name the document that has the DSMP. Alternatively, provide a description of the DSMP in the text box below. For guidance on developing a DSMP, review the [ITHS webpage on Data and Safety Monitoring Plans](#).

DSMP is uploaded to Zipline, in the 'Other attachments' section of the "Local Site Documents" SmartForm.

10.7. Un-blinding. If this is a double-blinded or single-blinded study in which the participant and/or relevant study team members do not know the group to which the participant is assigned, describe the circumstances under which un-blinding would be necessary, and to whom the un-blinded information would be provided.

This is not a blind study.

10.8. Withdrawal of participants. If applicable, describe the anticipated circumstances under which participants will be withdrawn from the research without their consent. Also, describe any procedures for orderly withdrawal of a participant, regardless of the reason, including whether it will involve partial withdrawal from procedures and any intervention but continued data collection or long-term follow-up.

If anytime the hospitalists decide subjects need to be on IV insulin infusion, they are no longer eligible for this study. In this case, they will be withdrawn from the research without their consent.

If hospitalists do not feel comfortable with the calculator doses and these subjects are admitted after midnight (PI: [name] is unavailable for discussion), hospitalists will withdrawal the subject from the research without their consent.

If the subject has already been given insulin before the study dosage can be administered, they will be withdrawn from the study

10.9. [DETERMINATION] Anticipated direct benefits to participants. If there are any direct research-related benefits that some or all individual participants are likely to experience from taking part in the research, describe them below:

Do not include benefits to society or others, and do not include subject payment (if any). Examples: medical benefits such as laboratory tests (if subjects receive the results); psychological resources made available to participants; training or education that is provided.

Participating in this study has the potential to achieve inpatient glycemic goal of 100-180 mg/dL faster than the standard of care with less manual adjustment.

10.10. [DETERMINATION] Return of individual research results.

Document Date & Version

06.29.2023

Version 4.6

APPLICATION IRB Protocol

Researcher Date & Version

mm/dd/yyyy

Version x.x

Page 50 of 55

In this section, provide your plans for the return of individual results. An “individual research result” is any information collected, generated or discovered in the course of a research study that is linked to the identity of a research participant. These may be results from screening procedures, results that are actively sought for purposes of the study, results that are discovered unintentionally, or after analysis of the collected data and/or results has been completed.

Review the guidance on [Return of Individual Results](#) for information about results that should and should not be returned, validity of results, the Clinical Laboratory Improvement Amendment (CLIA), consent requirements and communicating results.

10.10.a. Is it anticipated that the research will produce any individual research results that are clinically actionable?

“Clinically actionable” means that there are established therapeutic or preventive interventions or other available actions that have the potential to change the clinical course of the disease/condition or lead to an improved health outcome.

In general, every effort should be made to offer results that are clinically actionable, valid and pose life-threatening or severe health consequences if not treated or addressed quickly. Other clinically actionable results should be offered if this can be accomplished without compromising the research.

☒ **No**

☐ **Yes** → Answer the following questions (10.10.a.1 through 10.10.a.3.)

10.10.a.1. Describe the clinically actionable results that are anticipated and explain which results, if any, could be urgent (i.e., because they pose life-threatening or severe health consequences if not treated or addressed quickly).

Examples of urgent results include very high calcium levels, highly elevated liver function test results, positive results for reportable STDs.

Click or tap here to enter text.

10.10.a.2. Explain which of these results will be offered to subjects.

Click or tap here to enter text.

10.10.a.3. Explain which results will not be offered to subjects and provide the rationale for not offering these results.

Reasons not to offer the results might include:

- *There are serious questions regarding validity or reliability*
- *Returning the results has the potential to cause bias*
- *There are insufficient resources to communicate the results effectively and appropriately*
- *Knowledge of the result could cause psychosocial harm to subjects*

Click or tap here to enter text.

10.10.b. Is there a plan for offering subjects any results that are not clinically actionable?

Examples: non-actionable genetic results, clinical tests in the normal range, experimental and/or uncertain results.

☒ **No**

- ☐ **Yes** → Explain which results will be offered to subjects and provide the rationale for offering these results.

Click or tap here to enter text.

10.10.c. Describe the validity and reliability of any results that will be offered to subjects.

The IRB will consider evidence of validity such as studies demonstrating diagnostic, prognostic, or predictive value, use of confirmatory testing, and quality management systems.

The results will not be offered to subjects.

10.10.d. Describe the process for communicating results to subjects and facilitating understanding of the results. In the description, include who will approach the participant with regard to the offer of results, who will communicate the result (if different), the circumstances, timing, and communication methods that will be used.

The results will not be offered to subjects.

10.10.e. Describe any plans to share results with family members (e.g., in the event a subject becomes incapacitated or deceased).

The results will not be offered to family members.

10.10.f. Check the box to indicate that any plans for return of individual research results have been described in the consent document. If there are no plans to provide results to participants, this should be stated in the consent form.

Review the guidance on [Return of Individual Results](#) for information about consent requirements.

☐ **Confirmed**

10.11. Commercial products or patents. Is it possible that a commercial product or patent could result from this study?

☒ **No**

☐ **Yes** → Describe whether subjects might receive any remuneration/compensation and, if yes, how the amount will be determined.

Click or tap here to enter text.

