We plan to extract data from the inpatient Electronic Medical Record (EMR), including demographic characteristics (age, gender, race, weight, height), diabetes history (diabetes type, home antidiabetic medications), vital signs, laboratory measurements (POC BG and laboratory venous BG, latest hemoglobin A1c, renal function), interventions (inpatient insulin dose and modality, glucocorticoid, pain medication, surgery or procedure), nutrition status (oral intake, tube feed, intravenous dextrose), and hospital admission/discharge dates.

Our UW observational cohort (STUDY00015475) has 1/140 patients (0.7%) who had hypoglycemia < 54 mg/dL during the first 24 hours of hospitalization. We think (and from prior inpatient glycemic trials) 3% increase (which means 3.7%) is considered clinically significant increase, so among these 85 subjects there cannot be more than $85 \times 3.7\% = 3.15$ subjects that develop hypoglycemia < 54 mg/dL. So, if we find more than 3.15 patients (round to 4) who develop BG < 54 during the recruitment, that is more than 3% increase. Because this is the first feasibility trial to apply the calculator on patients, we plan to enroll 10 subjects first, to demonstrate the calculator dose does not cause hypoglycemia (≤ 54 mg/dL). After these 10 participants are recruited, we will review and analyze these data. Then we will apply for a modification to increase the sample size.

To examine the feasibility, the specific outcomes that will be measured are hypoglycemia (< 54 mg/dL), mean BG during the first 24 hours of hospitalization, and hyperglycemia (≥ 300 mg/dL), compared to our UW observational cohort ([STUDY00015475](#)).

The International Hypoglycemia Study Group defined three levels of hypoglycemia for the purpose of standardized reporting: BG < 70 mg/dL (level 1), < 54 mg/dL (level 2), < 40 mg/dL (level 3) [1]. Centers for Medicare & Medicaid Services (CMS) use the same definition to capture hospital glycemic data [2]. BG < 54 mg/dL was defined as clinically significant hypoglycemia and used in prior inpatient glycemic trials [3].

For statistical analyses, trial subjects (single-arm study with utilization of the insulin calculator) will be compared with the UW observational cohort (STUDY00015475) where standard of care was used (mostly by physicians' experience). The primary endpoint is hypoglycemia < 54 mg/dL. The secondary endpoint is mean BG during the first 24 hours of hospitalization and hyperglycemia (≥ 300 mg/dL).

Reference

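### The four-event hypoglycemia limit is set for 85 subjects but counted throughout recruitment, so between the 10-subject review and full enrolment no stated limit scales with the number dosed

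*Combined protocol and SAP*

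**What the plan says.** Section 10.1 starts from the comparison cohort: "Our UW observational cohort (STUDY00015475) has 1/140 patients (0.7%) who had hypoglycemia < 54 mg/dL during the first 24 hours of hospitalization". It then sets the margin: "We think 3% increase (which means 3.7%) is considered clinically significant increase". The limit is worked out on the full sample, "so among these 85 subjects there cannot be more than" 3.15 with an event, and is then read as a running count: "if we find more than 3.15 patients (round to 4) who develop BG < 54 during the recruitment, that is more than 3% increase". Section 5.1 gives the same limit. Section 1.5 states the criterion as a rate, not a count: hypoglycemia may not be 3% higher than in the cohort.

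Both 5.1 and 10.1 also describe a first stage: "we plan to enroll 10 subjects first, to demonstrate the calculator dose does not cause hypoglycemia". The stage ends with a review, "After these 10 participants are recruited, we will review and analyze these data", and then "Then we will apply for a modification to increase the sample size". No number of events is given that would pass or fail that review. Section 2.9 already lists 85 as the maximum number of subjects. Section 10.6 says that a data and safety monitoring plan (DSMP) was uploaded separately; its text is not among the supplied documents.

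**The concern.** The plan defines the unacceptable result as a rate, but the only number it monitors against is a count that equals this rate at about 85 subjects. Before then, a much higher observed rate can stay below the count. The text gives no limit for a smaller number dosed and names no look at the data between subject 10 and subject 85. It does not say what happens when the fourth event occurs.

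This matters because the trial exists mainly to test safety, hypoglycemia below 54 mg/dL is the primary endpoint, there is no control arm, and this is the first use of the calculator to dose patients. If the calculator overdoses, the cost is the number of further subjects exposed before anyone is required to look.

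**Working it through.** **Inputs (sections 5.1 and 10.1).** Cohort rate 1/140 = 0.71%. Limit 0.7% + 3 points = 3.7%. Planned sample 85. First stage 10 subjects.

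**1. The plan's own figure.** 85 × 0.037 = 3.145, which the plan gives as 3.15. The first whole number above it is 4. Check: 4/85 = 4.7% exceeds 3.7% and 3/85 = 3.5% does not. The figure is reproduced.

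**2. Where the count departs from the rate.** The observed rate k/n exceeds 3.7% as long as n < k/0.037:
- 1 event: up to n = 27 (1/27 = 3.704%)
- 2 events: up to n = 54 (2/54 = 3.704%)
- 3 events: up to n = 81 (3/81 = 3.704%)

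Four events are needed to exceed 3.7% only from n = 82 to 85. A crude rate just above 3.7% in a few subjects is weak evidence, so step 3 uses exact probabilities.

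**3. Three events in 20.** 3/20 = 15%. Exact binomial: P(X ≥ 3 | n = 20, p = 0.037) = 0.036. The exact one-sided 95% lower limit is 4.2%, above 3.7%; the two-sided 95% interval is 3.2% to 37.9% and just includes it. The count of 4 is not reached. If the true rate were 15%, P(X ≤ 3 | n = 20) = 0.65, so the count would more often than not still be unmet after 20 subjects.

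**4. What the 10-subject stage can catch.** The chance of no event in the first 10 is (1 − p)^10: 0.35 at a true rate of 10% and 0.20 at 15%. In those cases the stage passes on any reading, and only the count of 4 remains.

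**5. An illustrative scaled table.** Choose the largest n for which P(X ≥ k | n, 3.7%) ≤ 0.10:
- k = 2: n = 14 gives 0.093, n = 15 gives 0.105
- k = 3: n = 30 gives 0.098, n = 31 gives 0.106

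The same criterion does not give 4 events at any time: the tail for 4 events is 0.095 at n = 47, 0.101 at n = 48 and 0.386 at n = 85. The cap of 4 is therefore kept as the sponsor's own limit for n = 85 and is not derived from the 0.10 level.

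**6. Effect on mean enrolment.** Exact recursion over subjects 1 to 85. Assumptions: subjects are independent, each outcome is known before the next subject is dosed, and enrolment ends when a limit is met. The text does not fix how binding the 10-subject review is, so both ends are shown.

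| 10-subject review | Rule | True rate 10% | 15% | 20% |
|---|---|---|---|---|
| Blocks nothing | count of 4 only | 39.7 | 26.7 | 20.0 |
| Blocks nothing | scaled table plus cap of 4 | 29.2 | 16.6 | 11.2 |
| Any event blocks expansion | count of 4 only | 23.7 | 15.2 | 11.9 |
| Any event blocks expansion | scaled table plus cap of 4 | 21.5 | 12.7 | 9.2 |

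**7. Cost if the calculator is as safe as the cohort.** At p = 1/140, with no block at 10 subjects, the chance of meeting a limit by n = 85 is 0.33% with the count of 4 and 0.77% with the scaled table. The difference is 0.77 − 0.33 = 0.44 points.

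**The case against.** The strongest reply is that the plan already has an early safeguard in the same paragraph: 10 subjects, a review, and a modification before the sample is enlarged. This stands, and it rules out a reading that a reader might otherwise take from the fixed count, namely that 3 events in the first 10 would go unremarked and that enrolment would simply run on to the fourth event. Three events there would contradict the stage's stated aim and would be seen before expansion. If any event blocks expansion, most of the protection is already in place, as the lower half of the table shows. What the reply does not cover is subjects 11 to 85, or the missing criterion for the review itself.

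A second reply is that the arithmetic is correct. This also stands. Four events guarantee a final rate above 3.7% of 85, so the quoted sentence is true at any enrolment up to 85. The documents do not support calling it a miscalculation; the weakness is low sensitivity before full enrolment.

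Third, the text attaches no pause or stop to the fourth event, so treating it as a stopping rule is an interpretation. That is fair. It also means that the one numeric limit has no stated consequence.

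Fourth, the DSMP may contain interim looks or boundaries. It may, so the finding is confined to the text of 5.1 and 10.1, which would in any case have to agree with it.

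**Conclusion.** The point holds in a limited form. The limit of 4 is sound as a cap on the final total and insensitive as a running limit. From subject 11 onward it is the only numeric limit in the supplied text, and 3 events in 20 subjects, about four times the 3.7% rate, would stay below it. The 10-subject review is a real look, but it has no numeric criterion, and it is unclear how binding it is, since section 2.9 already gives 85 as the maximum.

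The size of the gain depends on that review. If any event there blocks expansion, a scaled table saves about 2 to 3 subjects on average at true rates of 10% to 20%. If it blocks nothing, the saving is about 9 to 10. These figures rest on the assumptions in step 6. The true rates are chosen for illustration, and the 0.10 level is a choice, not a figure from the plan. The conclusion would change if the DSMP already contains a limit scaled to enrolment.

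**What to change.** 1. Keep 4 events as the overall cap, described as the 3.7% limit applied to 85 subjects.
2. Add to 5.1 and 10.1 a short table by number of subjects dosed that prompts a pause in enrolment for safety review, for example 2 events within the first 14 and 3 within the first 30 (each with an exact tail of at most 0.10 at 3.7%). State what follows when an entry in the table, or the cap, is met.
3. State the numeric criterion for the 10-subject review, and whether enrolment waits for it.
4. Reconcile the endpoint definition: the 10-subject stage uses ≤ 54 mg/dL, while the limit and the primary endpoint use < 54 mg/dL.
5. Align the table with the DSMP. If the DSMP already holds such limits, cite them in 5.1 and 10.1.

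The cost is a few lines of protocol text and at most about 0.4 percentage points more chance of an unnecessary pause at the cohort rate (0.33% to 0.77%). The sample size and the 3.7% limit do not change.
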